CARBON MONOXIDE BREATH SENSOR SYSTEM (COBSS) PERFORMANCE, HUMAN FACTORS, AND USABILITY

PROTOCOL PROTOCOL PROTOCOL NUMBER:

ISSUE DATE:
FEBRUARY 15, 2017

Prepared By:	
Sr. Director, Clinical and Medical Affairs, Carrot S	ense, Inc.
Approved By:	
	_
	_
President and CEO, Carrot Sense, Inc.	
Tresident and CLO, Carrot Sense, Inc.	
	_
Chief Operating Officer, Carrot Sense, Inc.	_
Principal,	Date

Device Names	 Carbon Monoxide Breath Sensor System (COBSS) Bedfont Scientific Ltd. Micro+ Smokerlyzer
Protocol Title	Carbon Monoxide Breath Sensor System (COBSS) Performance, Human Factors, and Usability Study Protocol (COBSS)
Principal Investigators	
Protocol Number	
Protocol Version	
Protocol Shorten Name	Performance, Human Factors, and Usability Study Protocol
Study Design	Prospective, open label, single center clinical study enrolling 70 subjects. No medical decisions will be made related to test results.
Objective	 Performance: Non-invasively measure carbon monoxide (CO) levels in the exhaled breath of study subjects using two different types of measurement devices. We will assess the correlation between the measured CO levels (in parts per million, or ppm) of the study CO breath sensor (Carrot Sense) and the predicate CO breath sensor (Bedfont). Human Factors and Usability: Ensure that representative intended users are able to operate the COBSS independently. Validate appropriate mitigations of use related hazards identified in risk management documentation. Uncover previously unforeseen use errors.
Potential Subjects	70 subjects who self-report smoking 2 or more cigarettes each day.
Inclusion Criteria	18-80 years of age English speaking Owns and uses a smartphone Willing to sign the Informed Consent Form
Exclusion Criteria	Pregnancy
Recruitment	Eligible subjects will be identified via clinical research recruiter and advertisement at outdoor locations (i.e. flea markets, outside of movie theaters, shopping malls, train stations, stores that sell cigarettes), print media (i.e., local newspapers, billboards), and web media (i.e., Craigslist, Facebook).
Study Session	Single day study collecting 1 paired breath sample from each subject using two non-invasive breath sampling devices (COBSS and Bedfont; Performance), as

	well as conducting user tasks, user documentation assessment, subjective feedback and rating scales (Human Factors and Usability).
Performance Variable	CO concentrations in parts per million (ppm) in exhaled breath from subjects.

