9.3 ELIGIBILITY CRITERIA

The intended user population for the CO Breath Sensor System are lay users who are smokers, ages 18 and above, capable of using a smartphone to track/monitor health-related data. The intended users range in age, degree of smoking, mental and physical capabilities, health literacy, experience using other CO analyzers or home use medical devices, and experience using smartphones.

The user population may be further classified into two age-based subgroups, 18-49yr and the 50-80yr age groups. The 18-49yr olds, in general, are believed to be more tech savvy and have better physical capabilities compared to the 50-80yr olds.

Study participants will consist of individuals who represent the intended COBSS user profile, current smokers. Participant inclusion criteria include all of the following:

- 18+ years of age
- Current daily cigarette smokers (at least 2 cigarettes per day with target distribution of individuals who smoke: 2-5 cigarettes per day, 6-10 cigarettes per day, 11-15 cigarettes per day and 16+ cigarettes per day)
- Resident of the United States
- Able to read and comprehend English
- Target a mix of male and female participants
- Target 35 participants in each of the two subgroups, the 18-49yr and the 50-80yr age groups, with at least 15 individuals in each group
- Currently own and use an Apple, Inc. iPhone iOS smartphone or an Android smartphone for at least one month (such that they are familiar with basic operations of the mobile platform)
- Willing to sign the Informed Consent Form

Exclusion Criteria

- Prior experience using the COBSS
- Not interested in quitting smoking
- Pregnancy

Study participants will be recruited in the United States. Each potential participant will be asked a standard series of questions to confirm study eligibility and to capture demographic data. Eligible participants who meet the inclusion/exclusion criteria will be entered into the study. An

CONFIDENTIAL 19

Figure 5. Plot of paired CO (ppm) levels for Carrot Sense (CS) vs. Bedfont (Predicate)

_										_	
יו	\sim	0	n	m	1	01	n	t	N	lo	
	"	•	ш		ш			ı.	1	"	١

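### Do the different upper age limits and the shorter exclusion list in the synopsis leave eligibility undefined?

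*Combined protocol and SAP*

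**What the plan says.** The synopsis describes a "Prospective, open label, single center clinical study enrolling 70 subjects" and gives the inclusion criteria as "18-80 years of age English speaking Owns and uses a smartphone", plus willingness to sign the consent form. Its only exclusion is pregnancy.

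Section 9.3 is longer. It opens with a description of the product's users: "The intended user population for the CO Breath Sensor System are lay users who are smokers, ages 18 and above". It then says "The user population may be further classified into two age-based subgroups, 18-49yr and the 50-80yr age groups". The inclusion bullets that follow include "18+ years of age", "Resident of the United States" and "Able to read and comprehend English", a month or more of iPhone or Android use, and a recruitment aim: "Target 35 participants in each of the two subgroups, the 18-49yr and the 50-80yr age groups", with a minimum of 15 per group. The exclusions are earlier use of the study device, lack of interest in quitting, and pregnancy. Section 9.3 adds that candidates answer a standard set of screening questions and that those who meet the criteria are entered.

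**The concern.** Eligibility is a rule that the site has to apply, and two parts of one protocol state it differently. A synopsis may leave detail out, but here it adds an upper bound that the detailed section lacks, so shortening does not account for the age difference. Section 9.3 does not settle the matter either, because its own bullet is open-ended while its subgroups end at 80. A smoker aged 81 would be eligible under the bullet, ineligible under the synopsis, and in neither subgroup. Whether enrolling that person is a deviation, which Section 12.4 requires to be documented and analysed, would depend on the page consulted.

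The two exclusions absent from the synopsis matter in principle. Section 2.2 aims the usability assessment at untrained lay users, and Section 6.1.1 directs the device at smokers in cessation programs. A screener working from the synopsis alone could admit a previous user of the device or a smoker with no wish to quit, and the usability results would then rest partly on the wrong people.

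**Working it through.** No figure in the plan needs to be reproduced. The check is a comparison of text with some counting.

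**Age**

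| Place | Lower | Upper | Role of the line |
|---|---|---|---|
| Synopsis, inclusion | 18 | 80 | eligibility |
| 9.3, opening sentence | 18 | none | describes users of the product |
| 9.3, inclusion bullet | 18 | none | eligibility |
| 9.3, subgroups | 18 | 80 | recruitment aim |

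1. The second row is not a trial rule. A study may sample a narrower range than the product's eventual users, so it does not conflict with the synopsis.
2. The two eligibility lines overlap on ages 18 to 80. Enrolling only within that range satisfies both, since neither requires anyone over 80. They diverge only for a volunteer above 80.
3. The subgroup targets add to 35 + 35 = 70, the whole sample. That does not mean that no place exists for an older subject, because 35 is a target. The stated minimum fixes 15 + 15 = 30 places and leaves 70 − 30 = 40 not fixed by it. An over-80 volunteer is therefore possible, though not planned for.

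**Exclusions and wording**

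4. Section 9.3 has 3 exclusions and the synopsis 1, so 3 − 1 = 2 are omitted (earlier use of the device; lack of interest in quitting). One inclusion item, US residence, is also omitted, and the English-language and smartphone items are worded more loosely. On these five items the synopsis says less than Section 9.3. It nowhere says that the excluded people may be enrolled.
5. Screening is described in Section 9.3, beside the full list. Section 10 also records age, previous experience with CO breath sensors and desire to quit for every subject, so a wrongly admitted subject could be recognised.

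**What depends on it**

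6. Performance (Sections 9.5 and 12.2.2): each subject gives one pair of readings, one per device, and the criterion is a Pearson correlation over the pairs. Age group does not enter the visible text.
7. Usability (Sections 11.4 and 12.2.1): each task is rated per participant and judged against the use-related risk analysis. No comparison or pass rule by age group is visible.
8. The revision history mentions no eligibility change, and both lists are legible at these items.

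**The case for a change.** The strongest case for a change is that a protocol should state eligibility once, that the repair is a matter of wording, and that recording deviations under Section 12.4 does not say what counts as one. Treating Section 9.3 as controlling leaves its bullet and its subgroup labels at odds. The reading criterion also has substance here: subjects train themselves from written labelling and are later tested on the user documentation, so speaking English is a weaker condition than reading it. Nor can earlier users of the device be assumed away because it was not yet on the market: Section 9.4 refers to pilot data, so some may exist.

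The textual part of this stands: the age lines differ, and a careful editor would align them. The rest does not carry through to a result. Section 9.3 already contains the reading requirement and the exclusion of earlier users, and it is the section under which people are entered. An over-80 subject enrolled under it would be a smoker within the product's described user population, would supply a valid pair of readings, and could be described in the report by actual age. The lack of a subgroup label would matter only if an analysis used the labels, and none is visible.

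**Conclusion.** The concern is correct as a reading of the text but calls for no change to the plan. There is one clerical mismatch, in the upper age bound, which affects only a volunteer over 80. The other five differences (three omitted items and two looser wordings) are condensation in a synopsis whose full version is in Section 9.3. Following Section 9.3 as written would still give sound performance and usability conclusions, and so would enrolling only within the range that both eligibility lines share.

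This rests on three assumptions. First, the site screens from Section 9.3, as that section indicates. Second, few if any volunteers are over 80; the documents give no count. Third, the parts of Section 9.4 that cannot be read in the public copy contain no analysis by age group. If the third were wrong, placing an over-80 subject would need a decision, but only for that subject. The documents do not settle which upper limit was intended, and this review takes no position on it.

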1.0 LIST OF ABBREVIATIONS

CO Carbon Monoxide

COBSS Carbon Monoxide Breath Sensor System

CRF Case Report Form

BSA Breath Sensor Application

USB Universal Serial Bus

IRB Institutional Review BoardICF Informed Consent FormHCP Health Care Provider

ppm parts per million

2.0 Introduction

2 1	DAGREDOUND
Z. I	BACKGROUND

1 141	of tobacco products is a leading cause of preventable morbidity and mortality,
excess nearth of	care expenditure, and lost work productivity.

We have developed the Carbon Monoxide Breath
Sensor System (COBSS, Carrot Sense, Redwood City, CA, USA), which consists of a handheld
breath sensor to measure CO in exhaled breath, with results displayed in a smartphone app.
COBSS is intended to be used as a personal and mobile product and available 'over the counter'.
This study will compare the performance of the COBSS to that of a clinic-based CO breath
sensor (Micro+Smokelyzer; Bedfont; Kent, UK) in the measurement of CO in exhaled breath,

2.2 STUDY RATIONALE

and, will assess the human factors and usability of the COBSS.

Performance: We aim to non-invasively measure carbon monoxide (CO) levels in the exhaled breath of study subjects using two different types of measurement devices. We will assess the correlation between the measured CO levels (in ppm) of the study CO breath sensor (COBSS; Carrot Sense) completed by a lay user with no personal instruction (using labeling only) and the predicate CO breath sensor (Micro+Smokelyzer; Bedfont) administered by a person trained to instruct users on submitting a sample with the device.

Human Factors and Usability: We aim to assess whether an untrained lay user group (representative of intended users) can operate the device and interpret the results correctly using only the instructions that will be provided with the marketed device.

2.3 POTENTIAL RISKS AND BENEFITS

2.3.1 Known Potential Risks

There are no anticipated risks or harms to the subject. No medical decisions are made based on study data.

2.3.2 Known Potential Benefits

While we do not anticipate that subjects will receive any benefit from their participation in this study, it is possible that some subjects may experience an increased awareness of their smoking behavior.

2.3.3 Risk Benefit Assessment

Given the non-invasive nature of the breath sampling and the data collection, there are no anticipated risks to subject safety. Study staff will be with subjects and monitoring their use of the study devices for the duration of the study. Subjects are not asked to change their smoking behavior or lack thereof. No medical decisions are made based on study data.

3.0 OBJECTIVES

3.1 PERFORMANCE

We aim to non-invasively measure carbon monoxide (CO) levels in the exhaled breath of study subjects using two different types of measurement devices. We will assess the correlation between the measured CO levels (in ppm) of the study CO breath sensor (COBSS, Carrot Sense) and the predicate CO breath sensor (EC50 Micro⁺TM Smokerlyzer® – Bedfont (K082315)).

3.2 HUMAN FACTORS AND USABILITY

The objectives of the human factors and usability portion of the study are to:

- Ensure that representative intended users are able to operate the COBSS independently, focusing on the following:
 - o Proper breath sample collection using the CO Breath Sensor by a user
 - o User comprehension of how to navigate the Breath Sensor Application (BSA)
 - o User interpretation and comprehension of their results
- Validate appropriate mitigations of use related hazards identified in risk management documentation
- Uncover previously unforeseen use errors

Overall, this human factors and usability validation testing is conducted to demonstrate that the COBSS can be used by the intended users without serious use errors or problems, for the intended uses and under the expected use conditions.

4.0 REFERENCES

- FDA Guidance Document Entitled, "Guidance for Industry and Food and Drug Administration Staff: Applying Human Factors and Usability Engineering to Medical Devices," issued on February 3, 2016
- FDA Guidance Document Entitled, "Design Considerations for Devices Intended for Home Use, Guidance for Industry and Food and Drug Administration Staff" issued on November 24, 2014
- ISO/IEC 62366-1:2015, Medical devices Application of usability engineering to medical devices. Geneva, International Electro technical Commission.
- AAMI/ANSI HE75:2009, Human Factors Engineering Design of Medical Devices.
- https://www.bluetooth.com/what-is-bluetooth-technology/bluetooth-technology-basics

5.0 **DEFINITIONS**

Bluetooth Low Energy (BLE): a global wireless communication standard that connects devices together over a certain distance.

Breath Sensor Application (BSA): The smart phone application ("app") that is part of the subject system. The BSA displays exhaled breath carbon monoxide value to the user. The BSA is paired

CONFIDENTIAL 10

to the CO Breath Sensor via Bluetooth Low Energy.

Carbon Monoxide Breath Sensor System (COBSS): the name of the subject system. This system comprises the CO Breath Sensor and the Breath Sensor Application (BSA), and is intended for single-user use in smoking cessation programs as an educational and motivational tool showing how breath carbon monoxide levels are affected by smoking behavior.

Close Call (a.k.a. "Near-Miss"): Instances in which a user has difficulty or makes a use error that could result in harm, but the user takes an action to "recover" and prevents the harm from occurring (FDA Guidance 2016).

CO Breath Sensor: a component of the subject system. It is a personal mobile breath sensor that is capable of measuring the level of carbon monoxide (CO) in exhaled breath. The CO Breath Sensor is a portable, battery-powered, rechargeable device slightly smaller than the palm of one's hand. This device pairs to the Breath Sensor Application (BSA) on a smartphone via Bluetooth Low Energy. The user submits a breath sample by exhaling (blowing) into the personal mobile breath sensor via a provided straw.

Critical Task: A user task which, if performed incorrectly or not performed at all, would or could cause serious harm to the patient, user, or instrument, where harm is defined to include compromised medical care.

Guided Breath Test (GBT): a function in the BSA wherein the BSA prompts the user through the steps of submitting a breath test. Based on the user's adherence to the proper technique, the user is provided with a pass or fail. They may repeat this GBT as often as they like if additional education and reinforcement of the technique is desired.

Objective Data: Data collected through direct observation.

Subjective Data: Data collected through user feedback via comments, ratings, and assessments provided by participants.

Task: Action or set of actions performed by a user to achieve a specific goal.

Use Error: User action or lack of action that was different from that expected by the manufacturer and caused a result that (1) was different from the result expected by the user and (2) was not caused solely by device failure and (3) did or could result in harm. (Section 3.9, FDA Guidance 2016).

User: Person who interacts with (i.e., operates or handles) the COBSS.

6.0 DEVICE DESCRIPTION

6.1 CARBON MONOXIDE BREATH SENSOR SYSTEM (COBSS)

The Carbon Monoxide (CO) Breath Sensor System (COBSS) comprises a personal mobile breath sensor (CO Breath Sensor) capable of measuring the level of CO in exhaled breath and a Breath Sensor App (BSA) for smartphones which displays the exhaled breath CO value to the user. The BSA is compatible with iOS based devices (iPhone 5 and above, operating system iOS 9.0 and above) and Android based devices that support Bluetooth Low Energy (Android 4.4 and above,

CONFIDENTIAL

operating system Android 4.4 and above). Carrot Sense intends to market COBSS as a single-user over-the-counter (OTC) device indicated for use by smokers in smoking cessation programs as an educational and motivational tool showing how breath carbon monoxide levels are affected by smoking behavior.

6.1.1 Intended Use

The Carbon Monoxide Breath Sensor System (COBSS) is a breath carbon monoxide monitor intended for single-user use by smokers in smoking cessation programs as an educational and motivational tool showing how breath carbon monoxide levels are affected by smoking behavior.

6.2 MICRO+TM SMOKERLYZER®, PREDICATE DEVICE

The Micro^{+TM} Smokerlyzer® (Bedfont Scientific Ltd; Harrietsham, UK; 510K number: K082315) is an FDA-cleared hand-held, battery powered instrument which uses electrochemical technology to sample the gas and a microprocessor to convert the output from the sensor to a carbon monoxide (CO) concentration. The result and menus are displayed on a color LCD and an accompanying buzzer sounds in response to the CO level. The instrument is controlled using a touch screen operation. The range of CO measurement is 0-500 ppm

6.2.1 Indications for Use

The Micro⁺TM Smokerlyzer® is a Breath Carbon Monoxide Monitor intended for multi-patient use by healthcare professionals in smoking cessation programs and as an indicator of Carbon Monoxide poisoning in healthcare environments.

7.0 CARBON MONOXIDE BREATH SENSOR SYSTEM (COBSS)

7.1 LABELING AND PACKAGING

The CO Breath Sensor package includes:

- CO Breath Sensor with straw inserted
- 7 straws in a bag
- Micro USB charging cable
- User Manual
- Quick Start Guide
- Reference Card

The CO Breath Sensor packaging	The text to be included on
the package exterior is finalized however the final design of the package	ckage (text colors, font, etc.)
is in progress. The packaging used in the study will be the final des	igns.

Additional labeling includes the Guided Breath Test and video tutorial which are part of the BSA.

7.2 CO Breath Sensor

The CO Breath Sensor (Figure 1) is portable, battery-powered, and small enough to be conveniently carried by the user throughout the day (pocket, purse, backpack). The CO Breath Sensor is rechargeable using a micro-USB cable. The LED pulses orange while charging and then solid green when fully charged.

The CO Breath Sensor pairs to the BSA on the smartphone via low-energy Bluetooth. The user submits a breath sample by exhaling (blowing) into the CO Breath Sensor via a straw. The CO Breath Sensor comes packaged with a straw already inserted in the inlet. The straw, made of polypropylene, is reusable, and can be cleaned with soap and water or replaced as necessary. In addition, there is a pack of 7 straws (for 8 straws in total) included in the CO Breath Sensor package.

7.3 Breath Sensor Application (Pairing)

The BSA, Quick Start Guide and User Manual guide the first-time user through the process of pairing their smartphone to the CO Breath Sensor. Once paired, the CO Breath Sensor communicates exclusively with the user's phone and is invisible to other smartphones and other Bluetooth Low Energy wireless devices.

7.4 Breath Sensor Application (Getting Started)

After pairing, the BSA displays a Getting Started screen containing a brief video tutorial on how to submit a breath sample. This video depicts the user steps to submit a breath sample, as described in the User Manual. The BSA software automatically advances to and requires the user to complete the video tutorial after pairing. The video tutorial must be completed to advance further in the set-up and use of the BSA (system requirement). The video tutorial can be paused and played again. It is also accessible to the user at any time through the Settings screen in the BSA.

Next, a Guided Breath Test (GBT) function is used by the user wherein the BSA prompts the user through the steps of submitting a breath test (interactive version of the user steps disclosed in the User Manual). Based on the user's adherence to the proper technique, the GBT provides the user with a pass or fail. Pass or fail status is communicated to the user by the CO Breath Sensor LED (flashing green indicates pass and flashing red indicates fail), as well as the screen on the BSA, which includes a smiley face, flashing green dot and descriptive text for pass, or, a sad face, flashing red dot and descriptive text for fail

The BSA software requires the user to complete three GBTs before advancing further in

The BSA software requires the user to complete three GBTs before advancing further in the set-up and use of the BSA.

The user may repeat the GBT as often as they like if additional education and reinforcement of the technique is desired. The GBT is also accessible to the user at any time through the device button in the upper left corner of the CO Log screen in the BSA.

